6.4.4 Handling of Withdrawals

All withdrawals regardless of reason (whether the SCOUT PI or the parent removed the child from the study), will be followed-up by a phone call one week after their withdrawal to determine their status and if any medical follow up care was sought (in which case an MCN form will be completed).

The Study Coordinator will collect data from the treating physician by completing the Medical Care Notification (MCN) Form.

Symptomatic subjects that develop a positive urine culture will not be considered withdrawn from the study. They will continue to be seen/contacted for any remaining study visits as part of safety follow-up. These subjects cannot be re-enrolled into this study. For symptomatic subjects with positive urine culture and pyuria during the Day 6 - 10 period the study product will be discontinued. Symptomatic subjects with positive urine culture will be treated outside this protocol by a physician not associated with the SCOUT Study per current standard of care or if they prefer the parent(s)/legal guardian(s) can choose to have their child treated by their PCP/pediatrician.

Subjects that withdraw or are withdrawn from the study prior to being evaluable for the primary outcome measure will be replaced.

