12.2 Sample Size Considerations

The primary aim of this study is to determine if halting antimicrobial therapy in subjects that show clinical improvement 5 days after starting antibiotic therapy (short course therapy) is as effective as continued therapy through day 10 (standard course) as determined by treatment failure rate (symptomatic UTI) through TOC visit Day 11-14 (6-9 days after starting per protocol therapy).

The treatment failure rate under the standard of care, R_0 , is expected to be 5%. This estimate is based on data from previously published studies [43, 47]. The power and sample size calculations are based on the assumption that treatment failure under the short-course therapy, R_{SC} , will range from 5% to 9%.

In the non-inferiority test, on which power and sample size are based, the null hypothesis that short-course therapy is inferior to standard-of-care therapy is tested against the alternative that short-course therapy is non-inferior. That is, $H_0: R_{SC} > R_0 + \delta$ is tested against $H_a: R_{SC} \leq R_0 + \delta$, where δ is the “interval of equivalence,” the range

in which the treatment failure rates of the two therapies would be considered clinically equivalent. We believe that an interval of equivalence of 5% would be clinically acceptable; a success rate of 95% for the standard-of-care therapy group when compared to 90% for the short-course therapy group. For all power and sample size calculations, the significance level (chance of incorrectly failing to reject the null hypothesis) is $\alpha = 0.05$.

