Primary Analysis / Efficacy Analysis: The primary analysis will follow Intent-to-Treat (ITT) principles, with subjects analyzed according to randomized treatment assignment. In addition, a “per-protocol” analysis will be performed; the per-protocol analysis would include only subjects who were adherent to their assigned study regimen and completed 80% or more of the prescribed dose. All subjects taking at least one dose of study drug(s) who have been evaluated for treatment success at TOC visit or have failed treatment prior to TOC will be included in the ITT analysis (see the table below). The primary analysis will be a non-inferiority test comparing the number of symptomatic UTIs at the TOC visit between two treatment arms along with the 5% equivalence interval. The confidence interval of the difference in symptomatic UTI rates between the short-course and standard-of-care therapies will be calculated to evaluate whether this difference is less than or equal to the equivalence interval. This will be a one-sided test with $\alpha = 0.05$. Subjects with asymptomatic bacteriuria or who are asymptomatic with a

positive culture including pyuria will NOT be considered treatment failures for the primary outcome measure.

Table 9: SCOUT Study product Dosage Adherence

Antibiotic Drug	Antibiotic Dosage	80% of Expected Doses
Trimethoprim-Sulfamethoxazole (TMP-SMX)	8 mg/kg/day of Trimethoprim in 2 divided doses, Max 160mg BID Trimethoprim	Eight doses
Amoxicillin-Clavulanate*	45 mg/kg/day in 2 divided doses, Max 875 mg Q12H	Eight doses
Cefixime	8 mg/kg/day in 1 dose, Max 400 mg	Four doses
Cephalexin	50mg/kg/day in 3 divided doses	Twelve Doses

*Amoxicillin-clavulanate is no longer included as a study antibiotic, but subjects randomized to this treatment prior to its removal must have taken at least eight doses to be included in the per-protocol analysis.

Secondary Analysis:

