Safety Analysis: Safety in this study is related to efficacy. Safety will be evaluated by the collection and analysis of data on SAEs, clinical laboratory tests, pain assessments, and concomitant medications. The investigator is responsible for reporting all SAEs that are observed or reported up, regardless of their relationship to study product. Serious adverse events and abnormal laboratory (if available) results will be compared by treatment arm, with statistical tests for differences in proportion of subjects with serious adverse events between study arms.

Missing Data: Several procedures will be used to conduct data analysis when data for either outcomes or covariates are missing. The first step will be to assess the extent and pattern of missing data. If data are missing for only a few cases, then data analysis will be conducted only on study participants with complete data. However, when such a strategy would result in loss of data from a substantial proportion of participants or would lead to biased or inaccurate results, then some form of imputation will be performed. The form of imputation used will depend on the nature of the data that are missing.

Attrition and Loss to Follow-up: It is expected that loss to follow-up will be minimal in this study. Because the study is of short duration, we are hopeful that we will be able to follow virtually all subjects to study completion. However, some study participants may withdraw consent or may not return for the follow-up visits to determine the primary endpoint. Other participants may not have the endpoint determined due to problems with specimens or laboratory processing. We anticipate that these factors may reduce the sample size by as much as 10%. Thus the sample was increased by approximately 11% to offset this sample size reduction. Note that study participants who disrupt or discontinue study treatment will continue with follow-up and have the study endpoints assessed, and will be included in the ITT analysis.

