4.2.2 Primary/Efficacy analysis

The primary endpoint of this study is the proportion of children experiencing treatment failure (symptomatic UTI) at the TOC visit (Day 11-14).

The primary analysis will follow intent-to-treat (ITT) principles, with subjects analyzed according to randomized treatment assignment (*Table 3 in Section 7.1*). In addition, a “per-protocol” analysis will be performed; the per-protocol analysis would include only subjects who were adherent to their assigned study regimen and completed more than 80% of the prescribed dose (*Table 4 in Section 7.1*). All subjects taking at least one dose of study treatment between Day 6 and Day 10 who have been evaluated for treatment success at TOC visit or have failed before TOC will be included in the ITT analysis (See Table 4 below).

The primary analysis will be a non-inferiority test comparing the proportion of children with symptomatic UTIs at the TOC visit between two treatment arms to evaluate whether the difference is within the 5% equivalence interval. This test will be conducted by calculating the one-sided 95% upper confidence limit for the difference in symptomatic UTI (treatment failure) rates between the short-course and standard-of-care therapies. If this limit is less than or equal to the equivalence interval (0.05), then we will conclude that short course therapy is not inferior to standard therapy. Subjects with asymptomatic bacteriuria or who are asymptomatic with a positive culture including pyuria will NOT be considered treatment failures for the primary outcome measure.

Table 4: SCOUT Study Medication Dosage Adherence

Antibiotic Drug	Antibiotic Dosage	80% of Expected Doses
Trimethoprim-Sulfamethoxazole (TMP-SMX)	8 mg/kg/day of Trimethoprim in 2 divided doses, Max 160mg BID Trimethoprim	Eight doses
Amoxicillin-Clavulanate	45 mg/kg/day in 2 divided doses, Max 875 mg Q12H	Eight doses
Cefixime	8 mg/kg/day in 1 dose, Max 400 mg	Four doses
Cephalexin	50mg/kg/day in 3 divided doses	Twelve Doses

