4.2.6 Safety Analysis

Safety will be evaluated by the collection and analysis of data on (S)AEs. All (S)AEs will be reported, regardless of their relationship to study product (*Table 24 in Section 7.1*). The number of subjects with adverse events and the number of adverse events will be reported by body system and by treatment arm (*Table 24A-B in Section 7.1*). (S)AEs results (the number of subjects with adverse event and the number of adverse events) will be compared by treatment arm, with statistical tests for differences in proportion of subjects with serious adverse events between study arms. These analyses will use the ITT population and two-sided tests with significance level of 0.05 (*Table 25A in Section 7.1*).

Missing Data: Initially we will assess the extent and pattern of missing data using frequencies and cross-tabulations. If data are missing for only a few cases (5% or less), then data analysis will be conducted only on study participants with complete data. However, when such a strategy would result in loss of data from a substantial proportion of participants (i.e., 20%) or would lead to biased or inaccurate results, then sensitivity analysis or some form of imputation will be performed. The form of

imputation used will depend on the nature of the data that are missing. If data are missing for primary endpoint (treatment failure), frequencies for missing data by center, patient characteristic (clinical and demographic), and medication used will be examined. If there are significant associations of missingness with any of these characteristics, we would consider intent-to treat analysis with imputation methods such as regression technique, hot-deck, or best/worst case (for binary outcomes) and choose the one that would be most appropriate for type of missing data pattern (missing at random). If there is partial follow-up, that partial data might allow us to do an imputation. The imputation will be employed if there is a clear evidence of bias due to missing data. Sensitivity analyses will be performed to assess how sensitive results are to reasonable changes in the assumptions that are made for missing data.

To be considered evaluable a child must meet (a) below and one of (b) , (c) or (d):

(a) have taken study medication, AND;

(b) complete the Test of Cure visit, OR;

(c) have prior evidence of a treatment failure;

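### The set called ITT holds only dosed children with an observed primary outcome, and the SAP names no default method for the roughly 10% loss the plan expects

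*Protocol*

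**What the plan says.** **Analysis set.** Protocol 12.4 claims intent-to-treat principles for the primary analysis, then limits the set to "All subjects taking at least one dose of study drug(s) who have been evaluated for treatment success at TOC visit" or who failed treatment before that visit. SAP 4.2.2 repeats the rule, and SAP 5.1 labels the result Population 1, the ITT population.

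**Replacement.** Protocol 6.4.4: "Subjects that withdraw or are withdrawn from the study prior to being evaluable for the primary outcome measure will be replaced". SAP 2.4.2 agrees. Enrolment continues until the evaluable target is met: 672 of about 746 in protocol sections 5 and 6, and 652 of 724 in SAP 2.4.2.

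**Expected loss.** Protocol 12.4, on withdrawal, missed visits and specimen problems: "We anticipate that these factors may reduce the sample size by as much as 10" per cent.

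**Missing data.** The protocol gives no percentages. The SAP does, in the missing-data text under 4.2.6. Complete cases are used "If data are missing for only a few cases (5% or less". Sensitivity analysis or imputation follows when the loss is substantial, given as 20%, or when complete-case results would be biased or inaccurate. For a missing primary endpoint, the pattern is examined by centre, patient characteristics and medication. Imputation is considered if missingness is significantly associated with any of these, and the method is then picked from regression, hot-deck or best/worst case. The same text adds: "The imputation will be employed if there is a clear evidence of bias due to missing data". It also promises sensitivity analyses on the missing-data assumptions without saying which.

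**Outputs.** The main shells for the primary endpoint in SAP 7.1 are Table 3 (Population 1) and Table 4 (per protocol). No shell shows an imputed or sensitivity result.

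**The concern.** Membership of Population 1 depends on having an outcome, so the label promises more than the set delivers. A dosed child whose outcome is unknown leaves the denominator. Replacement restores the count but not the comparison that randomisation set up.

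The direction of any bias matters in a non-inferiority trial. If short-course children who are failing are more likely to be lost, the observed difference shrinks towards zero and the error favours the trial's claim. The protocol leaves a route for this. Treatment failure needs symptoms, pyuria and a positive culture (section 3), yet no urine is taken at an early termination visit before TOC, and a symptomatic child is referred to the primary care provider (8.6). Unless outside results are recovered, that child cannot be classified as a failure.

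The triggers do not guard against this. Associations between missingness and recorded characteristics cannot show whether the unseen outcomes differ, so the required evidence of bias may never appear even when bias is present. Imputation also has no defined set to act on, because Population 1 by construction contains no child without an outcome.

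**Working it through.** **Inputs.** Margin 5 points (protocol 12.2: "We believe that an interval of equivalence of 5% would be clinically acceptable"). One-sided alpha 0.05 (protocol 12.4). Non-inferiority is concluded when the one-sided 95% upper limit of the difference, short minus standard, does not exceed 0.05 (SAP 4.2.2). Planning rate 5% in both arms.

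**Reproducing the plan.** n per arm = (1.645 + 1.282)² × 2 × 0.05 × 0.95 / 0.05² = 325.4, so 326, as the SAP states for 90% power. The SAP's inflation: 326 × 1.11 = 361.9, stated as 362. The same factor gives 336 × 1.11 = 373.0, which is the protocol's 746 in total.

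**Where the expected loss falls.** 74/746 = 9.9% (protocol) and 72/724 = 9.9% (SAP). Both are above 5% and below 20%, so the planning case is the one without a default method.

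**Tipping point.** Unpooled Wald limit: U = (p1 − p0) + 1.645 × √[p1(1−p1)/n1 + p0(1−p0)/n0]. Assumptions: 336 observed and 37 missing per arm (373 − 336), 17 observed standard failures (5.1%), and 2 failures among the 37 missing standard children (5%), so standard is 19/373.

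| Observed failures, short v standard (of 336) | U, observed only | Missing short-course failures needed to lose non-inferiority | U at that point |
|---|---|---|---|
| 17 v 17 | 2.78 points | 10 of 37 | 5.04 points |
| 20 v 17 | 3.79 points | 7 of 37 | 5.04 points |
| 22 v 17 | 4.45 points | 5 of 37 | 5.04 points |

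Each row tips at 27/373 v 19/373: difference 2.145 points, standard error 1.760, and 2.145 + 1.645 × 1.760 = 5.04. At 26/373 the limit is 4.74, still non-inferior.

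**Equal failure among the missing.** From 17 v 17, if all 37 in each arm failed (54/373 v 54/373), the difference is 0 and U = 1.645 × 2.577 = 4.24 points; non-inferiority stands. From 20 v 17 it would take 35 of 37 failing in each arm to cross 5 points, and from 22 v 17 it would take 19 of 37.

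**Error rate under selective loss.** Suppose the true rates among all randomised children are 10% v 5%, exactly at the margin, 10% of the short arm is lost, and loss in the standard arm is unrelated to outcome. If lost short-course children fail at rate q, the observed short-course rate is (0.10 − 0.10q)/0.90. With 336 observed per arm:

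| q | Observed short-course rate | Chance of declaring non-inferiority |
|---|---|---|
| 20% | 8.9% | 14% |
| 30% | 7.8% | 32% |
| 40% | 6.7% | 58% |

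The nominal value is 5%. The documents give no failure rate for lost children, so q is an assumption throughout.

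**The case against.** The SAP is not silent. Its bias clause does not depend on the 20% figure, it names imputation methods, best/worst case marks the extremes of a tipping-point analysis, and its promise of sensitivity analyses carries no percentage or significance condition. A reader might infer that the plan has no provision for 10% loss. The documents do not support that. What remains is that the provisions are discretionary, unspecified and without an output.

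A reader might also infer that the trial rests on treatment completers, or that every child without a TOC outcome is replaced. Neither is right. Failures before TOC are kept, children who stop study product are followed and kept (protocol 12.4), and an asymptomatic child with no urine at TOC counts as a success (Table 2 footnote). The replacement text names withdrawals only; other losses are made up because enrolment runs to an evaluable target.

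Some failures may be recovered. Each withdrawn family is called after one week, with a Medical Care Notification form if care was sought (6.4.4), and urine results from the primary care provider can serve for endpoints during Days 6 to 10 (8.2). This reduces the risk without removing it.

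The illustration is also generous. Some of the 37 per arm may leave before any study dose, as entry failures (6.4.3) or because pending sensitivities show resistance (8.1). The documents do not give the split. If only 18 per arm were dosed, with 1 failing in standard (an assumption), 9 of 18 short-course children would have to fail from 17 v 17: 26/354 v 18/354, upper limit 5.24 points. Even 10 of 37 (27%) is about five times the rate assumed for the missing standard-arm children.

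**Conclusion.** The point holds in a limited form. The primary set is labelled ITT but is conditioned on an observed outcome, and for the loss the plan itself budgets the SAP fixes no default method. A stated analysis rule can therefore bias towards non-inferiority without the planned outputs showing it.

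The size depends on loss that differs by arm and is related to failure. With at most 37 missing per arm and 2 failing in standard, 10, 7 or 5 missing short-course failures reverse the conclusion from 17, 20 or 22 observed. Small loss, or loss with similar failure in both arms, would do little harm when the observed rates are close. The documents do not show that such selective loss will occur. The argument is that the analysis should reveal whether it could matter.

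**What to change.** Amend the SAP, with matching text in protocol 12.4:

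1. Rename Population 1 as the evaluable set.
2. Define the ITT set as every randomised child who took at least one dose of study product, including those later replaced.
3. Replace the 5%, 20% and evidence-of-bias triggers with one prespecified missing-outcome method, applied whatever the amount missing.
4. Always report a tipping-point analysis that varies the failure rate among missing children separately by arm, with its own table shell, and state whether non-inferiority holds in both sets.

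The fourth item does most of the work. Imputation under missing-at-random cannot address loss driven by the unseen outcome, and the available predictors are weak: every child is culture-positive at diagnosis and symptom-free at enrolment, and no urine is scheduled before TOC. If the method chosen in item 3 were to count every missing child as a failure, power at 373 per arm would fall to about 62% (failure rate 0.9 × 5% + 10% = 14.5% in both arms), against 91% with 336 evaluable per arm, so that choice should not be made by default.

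The cost is an SAP amendment, modest programming and a slightly wider interval. No extra patients are needed.

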The secondary outcome measures of this trial are provided above. A difference between the two arms with regards to asymptomatic bacteriuria, presence of clinical symptoms, and negative urine culture is not expected. No difference will mean that shorter courses of antibiotics for treatment are not inferior to long courses in eradicating bacteria from the urinary tract as well as impacting clinical symptoms. This analysis will be a conventional test for efficacy and will consist of a straightforward two-sample test for a difference between proportions, using a two-sided chi-square test at significance level of .05.

Sub-study Analysis:

Seattle Children’s Hospital R21

As previously noted, patient stool samples will be collected on 3 occasions. For primary analysis, cross-sectional analysis will be performed, i.e. looking at samples from one occasion at a time.

For each occasion, the following proportions will be summarized:

- 1) Among all patients, proportion of patients with *E. coli* detected, proportion of patients with *K. pneumoniae* detected, and same proportions within each treatment arm.
- 2) Among patients with *E. coli* detected, proportions of sub-type 0 or sub-type 1; among patients with *K. pneumoniae* detected, proportions of the two sub-types, and same proportions within each treatment arm.
- 3) Among patients with *E. coli* detected, proportions of treatment-susceptible *E. coli*; among patients with *K. pneumoniae* detected, proportion of treatment-susceptible *K. pneumoniae*; and same proportions for different treatment arms.
- 4) Among patients with *E. coli* detected AND treatment-susceptible, proportions of sub-type 1; among patients with *K. pneumoniae* detected AND treatment-susceptible, proportions of sub-type 1; and same proportions for different treatment arms
- 5) Among patients with *E. coli* detected proportion of treatment-resistant *E. coli*; among patients with *K. pneumoniae* detected, proportion of treatment-resistant *K. pneumoniae*; and same proportions within different treatment arms.

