4.2.3 Secondary analysis

The secondary endpoints include:

- a. The proportion of children experiencing a recurrent urinary tract infection at any time after the TOC visit.
- b. The proportion of children with asymptomatic bacteriuria at the TOC visit.
- c. The proportion of children that develop the gastrointestinal colonization of antimicrobial resistant *Escherichia coli* (*E. Coli*) and *Klebsiella pneumoniae* (*K. Pneumoniae*) assessed through Outcome Assessment visit (Day 24-30).
- d. The proportion of children presenting with clinical symptoms that may be related to UTI prior to or at the TOC visit.
- e. The proportion of children with positive urine culture prior to or at TOC visit.

The secondary analysis for recurrent infection (Table 5 in Section 7.1), asymptomatic bacteriuria (Table 6 in Section 7.1), presenting with clinical symptoms (Table 7 in Section 7.1), and positive urine culture (Table 8 in Section 7.1) (Endpoints a, b, d and e), will include conventional tests to evaluate whether the proportions between two treatment arms are equal. These tests will be conducted by calculating the two-sided 95% confidence limit for the difference between the short-course and standard-of-care therapies. Analyses will be performed on per-protocol population, with appropriate exclusions of treatment failures. Details of these exclusions are shown in Section 5.1.

The secondary analysis for proportion of children that become colonized with antibiotic-resistant *E. coli* and *Klebsiella pneumoniae* assessed through Outcome Assessment visit (Day 24-30) (Endpoint c) will consist of two-sample tests for differences between proportions, using a chi-square test at significance level of 0.05 (Table 9 in Section 7.1). We hypothesize that children with short-course therapy will be less likely to become colonized with emergent antibiotic-resistant *E. coli* and *K.*

pneumoniae. These analyses will examine whether antibiotic resistance after enrollment emerges differently between the short course and standard of care arms. First, a summary of antibiotic resistance present at enrollment, TOC and Outcome Assessment among the per-protocol population excluding treatment failures with a sample at TOC (Population 4) will be presented (*Table 9 in Section 7.1*).

Emergent antibiotic resistance will be defined as follows:

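### For three secondary endpoints the protocol reads absence of a difference on a two-sided chi-square test as non-inferiority, with no margin, and the SAP does not replace that reading

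*Protocol*

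**What the plan says.** Protocol 12.4 (Secondary Analysis) opens with the expectation for three of the five secondary endpoints: "A difference between the two arms with regards to asymptomatic bacteriuria, presence of clinical symptoms, and negative urine culture is not expected". It then gives the interpretation: "No difference will mean that shorter courses of antibiotics for treatment are not inferior to long courses in eradicating bacteria". The rest of that sentence extends the same reading to clinical symptoms. The analysis named next is a two-sample test for a difference in proportions, "using a two-sided chi-square test at significance level of .05".

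The 5% interval of equivalence in Protocol 12.2 is the range "in which the treatment failure rates of the two therapies would be considered clinically equivalent". It is defined for treatment failure only. Protocol 12.4 and SAP 4.2.2 apply it to the primary endpoint, where the SAP compares a one-sided 95% upper limit with 0.05.

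SAP 4.2.3 does not repeat the protocol's interpretive sentence. For recurrent infection and these three endpoints (a, b, d and e) it says the analysis "will include conventional tests to evaluate whether the proportions between two treatment arms are equal", carried out by "calculating the two-sided 95% confidence limit for the difference between the short-course and standard-of-care therapies". Table shells 6 to 8 show the difference and its limits for b, d and e. No margin is given for any of them.

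**The concern.** A test of equality and a test of non-inferiority answer different questions. A non-significant chi-square says only that the data are compatible with no difference; they may equally be compatible with a material excess on short course. To conclude non-inferiority, the upper confidence limit must fall below a margin fixed in advance. Without one, the chance of wrongly concluding non-inferiority is not controlled. It also rises as the sample shrinks, so imprecision is rewarded.

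At stake is the bacteriological claim. Asymptomatic bacteriuria does not count as treatment failure, so clearance of bacteria in asymptomatic children is judged only through the secondary endpoints. The protocol sentence would support a prespecified-looking statement that short course is not inferior in clearing bacteria and symptoms, on a result that may reflect only too few events.

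The point covers endpoints b, d and e. The sentence does not name recurrent infection (a) or resistant colonization (c).

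**Working it through.** **Inputs**
- Evaluable subjects: 672 (Protocol 5), so 336 per arm at 1:1; 652 (SAP 2.4.2), so 326 per arm.
- Secondary test: two-sided, 0.05, no margin (Protocol 12.4).
- Margin for treatment failure: 5 points (Protocol 12.2).
- Event rates and margins for b, d and e: none in the documents. Those used below are assumptions.

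**1. The plan's own figure.** For the primary endpoint at 90% power, n per arm = (z₀.₉₅ + z₀.₉₀)² × [R₀(1−R₀) + R_SC(1−R_SC)] / δ² = (1.6449 + 1.2816)² × (0.0475 + 0.0475) / 0.05² = 8.564 × 0.095 / 0.0025 = 325.4, rounded up to 326. This matches SAP 3.2. The documents contain no corresponding calculation for the secondary endpoints.

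**2. What a non-significant result can hide, with no margin assumed.** Take 336 per arm and find the largest short-course count that stays non-significant, using z = (p₁ − p₀) / √[2p̄(1−p̄)/n] against 1.96. The interval is (p₁ − p₀) ± 1.96 × √{[p₀(1−p₀) + p₁(1−p₁)]/n}.

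For 34 against 50: the difference is 16/336 = 0.0476 and p̄ = 84/672 = 0.125, so z = 0.0476 / √(2 × 0.125 × 0.875 / 336) = 0.0476 / 0.0255 = 1.87 and p = 0.062.

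| Standard events | Short-course events | Excess (points) | Upper two-sided 95% limit (points) |
|---|---|---|---|
| 17 (about 5%) | 29 | 3.6 | 7.4 |
| 34 (about 10%) | 50 | 4.8 | 9.75 |
| 50 (about 15%) | 69 | 5.7 | 11.4 |

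Under the protocol sentence each row would be read as not inferior.

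**3. Error rate, for illustration.** Suppose short course is truly 5 points worse and 5 points is the margin. The probability of a non-significant test, by exact enumeration of two binomials (uncorrected chi-square), is:

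| Standard-arm rate | 336 per arm | 326 per arm | 200 per arm (assumed) |
|---|---|---|---|
| 5% | 0.299 | 0.313 | 0.528 |
| 10% | 0.499 | 0.512 | 0.674 |
| 15% | 0.601 | 0.609 | 0.737 |

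Normal-approximation check at 5% against 10%, 336 per arm: power is about 0.692, so 1 − 0.692 = 0.308 against 0.299 exact.

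Over standard-arm rates of 2% to 30% at 336 per arm, the probability runs from 0.098 to 0.717. With a true excess and margin of 10 points it falls to 0.006, 0.043 and 0.148 at rates of 5%, 10% and 20%.

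**4. Comparison with a margin rule.** In the same 5-point scenarios at 336 per arm, requiring the upper two-sided 95% limit to be at most 5 points gives a wrong non-inferiority conclusion with probability 0.028, 0.026 and 0.026.

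**5. Does the SAP's interval change this?** If the interval is read only for whether it includes zero, the probabilities at 336 per arm are 0.296, 0.498 and 0.598, practically the same as the chi-square. The interval helps only if its upper end is interpreted.

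**The case against.** The protocol says no difference rather than a non-significant test, and states no explicit p-value rule for concluding non-inferiority. That is true, but the two-sided chi-square is the only means it gives for judging the matter, so the reading is fair.

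A stronger point is that Protocol 12.4 calls itself a general description and leaves details to the SAP. The SAP drops the sentence, plans confidence limits for these endpoints and has no p-value column in shells 6 to 8. A careful reader would see the imprecision. This reduces the harm. It does not remove it, because the SAP still describes tests of equality, gives no rule for reading the limits and does not replace the protocol's inference.

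The denominators above are also not those of the planned analysis. SAP 4.2.3 uses the per-protocol population, and the footnote to Protocol Table 2 makes asymptomatic children with no urine sample at the test-of-cure visit non-evaluable for bacteriuria and culture. The real numbers are probably smaller, which makes the problem worse, as the 200-per-arm column shows.

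Finally, the error rates in step 3 depend on a borrowed margin and assumed rates. For symptoms and culture, rates below about 5% are unlikely, because SAP 4.2.3 counts every treatment failure as positive for both and failure is expected at 5%. The counts in step 2 need no margin.

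**Conclusion.** The concern holds: the inference is wrong as written. At 336 per arm, observed excesses of 3.6 to 5.7 points, with upper limits of about 7 to 11 points, would be read as not inferior. If 5 points were the margin and standard-arm rates were 5% to 15%, the rule would wrongly declare non-inferiority about 30% to 60% of the time; with a 10-point margin the figure is about 1% to 15% at rates of 5% to 20%. These rates and margins are assumptions, but the logical fault does not depend on them. It affects the interpretation of three secondary endpoints only. The primary analysis, which compares a limit with a margin, the sample size and the halting rules are untouched. It should be fixed, but it does not threaten the trial's main conclusion.

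**What to change.** Delete the interpretive sentence from Protocol 12.4. State there and in SAP 4.2.3 that, for asymptomatic bacteriuria, clinical symptoms and positive urine culture, the difference and the two-sided 95% interval of shells 6 to 8 are reported, and that no non-inferiority conclusion is drawn from a non-significant test.

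The cost is wording only, since the intervals are already planned. The protocol change needs NIAID review and IRB approval (Protocol 15.2). If no amendment is otherwise due, the SAP sentence alone would secure most of the benefit. The downside is that some secondary results will be reported as inconclusive.

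Only if the sponsor wants a non-inferiority claim on these endpoints should a margin be prespecified and justified for each, together with the confidence level. The planned two-sided 95% limit corresponds to a one-sided 2.5% test, stricter than the primary's 5%. With a 5-point margin and that limit, the chance of success at truly equal rates with 336 per arm would be about 84%, 58% and 45% at rates of 5%, 10% and 15%.
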